8.3 Safety Variables

Safety will be evaluated by collecting information on adverse events and by routine assessments. All adverse events will be graded using the NCI CTCAE version 4.0 and recorded in the CRF.

Specific safety assessments include the following:

- ∞ Treatment emergent AEs graded according to NCI CTCAE v4. The frequency and severity of AEs will be evaluated following administration of oral ENMD-2076

- ∞ Change from Baseline in vital signs (blood pressure, heart rate, respiratory rate, and body temperature)
- ∞ Change from Baseline in clinical laboratory tests from baseline values obtained prior to treatment
- ∞ Change from Baseline in electrocardiograms (ECGs)

Serious adverse events require expedited reporting to the medical monitor as described in the protocol

8.3.1 Clinical Laboratory

Non-fasting blood and urine specimens for the measurement and evaluation of clinical chemistry, hematology/coagulation, urinalysis, and pregnancy hormones (female patients with childbearing potential) will be collected as described in Table 2. Approximately 20 mL of blood will be collected for the clinical laboratory assessments at the specified times. Serum pregnancy tests will be performed as described in [Table 4](#). A positive pregnancy test prior to dosing will exclude the patient from enrolment in the study. See [Section 8.3.7](#) for requirements regarding pregnancies during the study. Values for the following parameters will be obtained:

Table 2 Non-fasting blood and urine specimens (Measurements and evaluation of clinical chemistry, hematology/coagulation, urinalysis, and pregnancy hormones)

HEMATOLOGY	CLINICAL CHEMISTRY	URINALYSIS
Hemoglobin	Total protein	Color/appearance
Hematocrit	Albumin	Specific gravity
Platelet Count	Creatinine	pH
White Blood Cell Count	Uric acid	Protein (qualitative)*
Differential, including:	Bilirubin (conjugated and total)	Glucose (qualitative)
Neutrophils	Alkaline phosphatase	Ketones (qualitative)
Lymphocytes	AST(SGOT)	Bilirubin (qualitative)
Basophils	ALT (SGPT)	Blood (qualitative)
Monocytes	Glucose	Standard microscopic examination if above parameters are abnormal
Eosinophils	Calcium	
	Phosphorus	
COAGULATION TESTS		OTHER
Prothrombin time (PT) or International Normalized Ratio (INR)	Bicarbonate	Serum Pregnancy Test (according to study schedule)
Partial thromboplastin time (PTT)	Chloride	
	Sodium	
	Potassium	
	Magnesium	

* If Grade 2, then 24-urine must be obtained.

The results of clinical laboratory tests conducted during the study must be assessed by the Investigator to determine each patient's continuing eligibility for participation in the study. If values are outside the normal reference range, the Investigator must determine clinical significance within the context of the study and the patient's baseline. Clinically significant abnormal laboratory parameters occurring during the study are reported as AEs.

8.3.2 Medical History and Physical Examination

As part of the physical examination, a medical history will be taken with particular attention to (1) a review of the body systems, including diagnosis of malignancy; and (2) use of prescription medications, including prior chemotherapy and corticosteroids, and nonprescription medications.

Physical examination findings within the following categories will be assessed:

- HEENT
- pulmonary
- cardiovascular
- GI/abdomen
- extremities
- neurological
- skin and hair
- weight

The Screening Visit will also include measurement of height.

8.3.3 Standard 12-lead Electrocardiograms (ECGs)

A standard 12 Lead ECG will be performed at the times described in [Table 4](#). In the case of an abnormal ECG, the ECG should be repeated to rule out machine error or improper placement of leads and reviewed by a local cardiologist. Any abnormality determined to be clinically significant by the Investigator should be discussed with the Medical Monitor prior to enrolment of the patient.

Any ECGs deemed abnormal by the Investigator may be over read by a cardiologist to make a determination of clinical significance. In some cases, it may be appropriate to repeat abnormal ECGs to rule out improper lead placement as contributing to the ECG abnormality. It is important that leads are placed in the same positions each time in order to achieve precise ECG recordings.

8.3.4 Vital Signs

Vital signs include systolic and diastolic blood pressure, heart rate, respiratory rate, and body temperature. These parameters will be measured as described in [Table 4](#). Vital sign measurements will be conducted after several minutes in the sitting position.

8.3.5 ECOG Performance Status

The Investigator will assess each patient's functional status using the ECOG Performance Status Scale at the time points identified in [Table 4](#). Eligible patients must have an ECOG Performance Status of 0 to 2 at screening (see [Appendix B](#)).

8.3.6 Adverse Events

8.3.6.1 Adverse Events (AE) and Serious Adverse Events (SAE)

An adverse event (AE) is any untoward medical occurrence in a subject participating in a clinical trial. An adverse event can be any unfavorable and unintended sign, symptom or disease

temporally associated with the use of the study medication, whether or not considered related to the study medication. AEs will be collected from the start of treatment until 30 days following the final visit dose. Any events occurring prior to treatment will be recorded on the medical history page with the event name and onset date and end date if not continuing. Pre-existing, known clinically significant conditions observed at screening should be recorded as medical history.

This definition also includes accidental injuries, reasons for any change in medication (drug and/or dose) other than planned titration, reasons for admission to a hospital, or reasons for surgical procedures (unless for minor elective surgery for a pre-existing condition). It also includes adverse events commonly observed and adverse events anticipated based on the pharmacological effect of the study medication. Any new laboratory abnormality assessed as clinically significant by the Investigator must be recorded as an adverse event.

A treatment emergent adverse event is any adverse event occurring after start of study medication and within the time of residual drug effect, or a pre-treatment adverse event or pre-existing medical condition that worsens in intensity after start of study medication and within the time of residual drug effect.

Adverse events should be recorded as diagnoses, if available. If not, separate sign(s) and symptom(s) are recorded. One diagnosis/symptom should be entered per record.

Note that death is not an event, but the cause of death is. An exception is the event of sudden death of unknown cause. Note that hospitalization is not an event; however, the reason for hospitalization is. Procedures are not events; the reasons for conducting the procedures are. In general, only the reason for conducting the procedure will be captured as an adverse event. However, if deemed necessary by the Investigator, a procedure can be captured along with the reason for conducting the procedure.

An overdose or medication error is not an adverse event unless it is temporally associated with an unfavourable or unintended sign or symptom.

Each AE is to be classified by the investigator as serious or non-serious. A serious adverse event (SAE) is any untoward medical occurrence or effect that occurs at any dose:

- ∞ Results in death
- ∞ Is life-threatening (i.e., an immediate risk of death)
- ∞ Requires in-patient hospitalization or prolongation of existing hospitalization
- ∞ Results in persistent or significant disability/incapacity
- ∞ Is associated with a congenital anomaly/birth defect
- ∞ Is an important medical event

An adverse event caused by an overdose or medication error is considered serious if a criterion listed in the definition above is fulfilled.

Important adverse events that may not result in death, may not be life-threatening, or do not require hospitalization may be considered serious when, based upon appropriate medical judgment, they may jeopardize the subject's safety or may require medical or surgical intervention to prevent one of the outcomes listed above.

Serious adverse events also include any other event that the investigator or sponsor judges to be serious or which is defined as serious by the regulatory agency.

The investigator is to report all directly observed adverse events and all adverse events spontaneously reported by the trial subject using concise medical terminology. In addition, each trial subject will be questioned about adverse events. The question asked will be "Since you began taking the study medication, have you had any health problems?"

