8.2 Secondary Efficacy Variables

- ∞ 6-month progression free survival (PSF6) rate
- ∞ The median PFS and TTP as based on RECIST 1.1 and measured by time from first study drug administration until progression or death.
- ∞ The median Overall survival as measured by time from first study drug administration to death or study completion.
- ∞ Safety data will be collected from time of informed consent through study completion /withdrawal up to 30 days after the last dose of study medication by each subject.

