8.3.6.4 Reporting of Serious Adverse Events

An AE that is serious or potentially serious requires the following additional detailed reports and follow-up and should be recorded in the CRF. The content of these detailed reports should address the Investigator's (or in some cases, the Sponsor's) estimate of causality, and whether or not the AE is identified in nature, severity, and frequency in the [Investigator's Brochure](#) or in other risk information that has been supplied to the Investigator.

Sponsor Notification

Any SAE that occurs after starting study drug administration must be reported to the Clinical Study Monitor or Project Manager as soon as information is available. In turn, the Clinical Study Monitor/Project Manager must immediately inform the Medical Monitor of the event and document the notification in a telephone/contact report. The urgency for reporting a SAE is three-fold: (1) to facilitate discussion (and implementation, if necessary) by the Sponsor and the Investigator of appropriate follow-up measures; (2) to facilitate Investigator reporting of unanticipated problems involving risk to human patients to the IRB/REB; and (3) to enable the Sponsor to fulfil the requirements to the appropriate regulatory authority.

Any non-fatal or non-life-threatening SAE, regardless of expectedness or causality, or fatal or life-threatening SAE must be immediately reported to the Clinical Study Monitor or Project Manager by telephone or facsimile, and a written report (Serious AE Report Form) signed by the Investigator must be provided to the Clinical Study Monitor or Project Manager promptly, but no later than the timelines outlined in Table . This documentation will be forwarded to the Medical Monitor immediately to facilitate the prompt detection by the Medical Monitor of any changes in the nature, severity, or frequency of serious AEs, and allow the Sponsor to meet reporting requirements of the appropriate regulatory agency.

Table 3 Serious Adverse Event Reporting Requirements for Protocol 2076-CL-006

Communication	Initial Reports		Follow-Up Reports
	Fatal or Life-Threatening SAE	Other SAEs	Any SAE
Vendor SAE Portal*/ Telephone/Fax/Email	Immediately** Vendor SAE Portal*/ Telephone/Fax	Within 24 hours** Vendor SAE Portal*/ Telephone/Fax/Email	Prompt notification required no later than 48 hours** Update Vendor SAE Portal
Written	Within 48 hours** Vendor SAE Portal	Within 48 hours** Vendor SAE Portal	

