9.2.3 Genomic testing

Paraffin embedded tumor tissue sections and one whole blood sample will be collected and processed for a 410 gene panel DNA sequencing analyses. The treatment and preservation of

tumor tissue will follow the routine operation procedures in pathology. Tissue blocks with high levels of tumor cells should be selected (weight 100~500 mg, diameter >5 mm). At least 15-20 unstained and charged slides should be provided, with a thickness of 10 μ m, along with one HE stained paraffin sections with a thickness of 5 μ m. Slides should be cut from the same source. The predicted tumor cells should be more than 50%. The tissue section samples will be shipped to MSKCC after collection for further testing and analysis. The tumor cell DNA will be extracted, sequenced and analyzed based on standard operational procedures at the MSKCC research laboratory. One whole blood sample should be collected in a 3mL EDTA lavender top tube and send to MSKCC. MSKCC's Center of Molecular Oncology will run its Integrated Mutation Profiling of Actionable Cancer Targets (IMPACT) battery of 410 cancer genes on all samples provided. This information will be collected for research purposes only.

9.2.4 Tumor biopsy:

Tumor biopsies will be performed as per local institutional guidelines. Tumor biopsy (optional) baseline up to 30 days prior to initiation of dosing (if patient had a biopsy after any previous treatments, they would be exempt of this biopsy) and at the end of treatment Cycle 2 (or Day 1 of cycle 3) in line with the imaging for tumor measurement. An additional optional biopsy at the time of disease progression will be performed in patients who have complete response, partial response or stable disease for > 16 weeks. If either the baseline or post-treatment biopsy is unable to be obtained due to technical issues (after consenting the patient and making a reasonable effort), the patient is still eligible to participate in the study. A third optional biopsy will take place at the time of disease progression for patients who have complete response, partial response, or stable disease for \geq 16 weeks. Biopsy samples obtained pre- or after treatment will also be used for biomarker analysis using immunohistochemistry methods as described above. For tissue biopsy, multiple strips that are sufficient for biomarker study should be provided.

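### The plan gives no single start point for safety capture, and under its AE and SAE sections a complication of the optional pre-dose biopsy is recorded only as medical history unless it worsens on treatment

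*Combined protocol and SAP*

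**What the plan says.** Five places in the combined protocol and SAP bear on when safety capture starts.

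- Synopsis and 8.2: "Safety data will be collected from time of informed consent through study completion". The term used is safety data; AEs and SAEs are not named.
- 8.3.6.1: "AEs will be collected from the start of treatment until 30 days following the final visit dose". For anything earlier, "Any events occurring prior to treatment will be recorded on the medical history page", with a name and onset and end dates.
- 8.3.6.4: "Any SAE that occurs after starting study drug administration must be reported to the Clinical Study Monitor or Project Manager".
- Table 4: the AE monitoring row is blank at Screening and first marked at Baseline, Day 1 before the dose. Footnote h says that monitoring is continual for patients on study.
- 8.3.6.3: every AE arising in the study is to be reported, with no first-dose limit and regardless of relation to drug.

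The scripted question in 8.3.6.1 also looks back only to first dose: "Since you began taking the study medication, have you had any health problems".

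One invasive study procedure falls in the disputed period. Section 9.2.4 describes it as "Tumor biopsy (optional) baseline up to 30 days prior to initiation of dosing", and Table 4 marks it at Screening for biomarker work. It is waived in one case: "if patient had a biopsy after any previous treatments, they would be exempt of this biopsy". For minors it needs a medical indication.

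**The concern.** A site cannot tell from these sections whether an event between consent and first dose is an AE. The most specific instructions (the collection rule, the SAE rule and the scripted question) all point to first dose, so a site may well follow those. A complication of a biopsy done for the trial would then be filed with background conditions.

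Two things are at stake. First, harm caused by a trial procedure could go without a grade, a seriousness or causality assessment, or sponsor notification. Second, the notification chain in 8.3.6.4, from study monitor to Medical Monitor with parallel IRB notice, is started by an SAE. An entry on the medical history page has no defined trigger for it.

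**Working it through.** There is no plan figure to reproduce. The check compares the rules and then follows one event through them.

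**Step 1: the rules for an event after consent and before first dose.**

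| Source | Treatment of the event |
|---|---|
| Synopsis, 8.2 | Within safety data; AE status not stated |
| 8.3.6.1 | Not collected as an AE; medical history page |
| 8.3.6.3 | If an AE, reported, graded, assessed for causality; SAE form if serious |
| 8.3.6.4 | No SAE report required |
| Table 4 | No AE monitoring at Screening; starts at pre-dose Baseline |

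Table 4 and 8.3.6.1 disagree even on Day 1, because the table monitors AEs before the dose and the text does not. Section 8.3.6.1 is also awkward within itself: its treatment-emergent definition refers to pre-treatment AEs that worsen, a category that its own collection rule does not create.

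**Step 2: length of the window.** Screening runs from Day -28 to Day 1, so up to 28 days. The baseline biopsy may be up to 30 days before dosing, which is 30 - 28 = 2 days longer than the screening period. The longest interval from study biopsy to first dose is therefore 30 days.

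**Step 3: a biopsy complication, if 8.3.6.1 and 8.3.6.4 govern.**

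| Course | Result |
|---|---|
| Resolves before first dose | Medical history only |
| Prevents dosing | Medical history only; outside the safety population, which 10.1 limits to patients with at least one dose |
| Continues unchanged after first dose | Medical history only |
| Worsens after first dose | Treatment-emergent AE by 8.3.6.1; reported under 10.5.1 |

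Only the last course reaches the AE tables. Section 10.7 provides a CRF for each screened patient, so an undosed patient would leave a record, but not one that 10.1 brings into the safety analysis.

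**Step 4: whether the worsening route works.** Worsening is a change in intensity, so it needs a starting grade. Section 8.3.6.3 requires a CTCAE grade for each AE. For the medical history page, 8.3.6.1 specifies only a name and dates. The pre-dose grade needed for the comparison is therefore not specified.

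**Step 5: exceptions.** No section excepts events caused by study procedures from the first-dose rule. Biopsies after Cycle 2 and at progression come after first dose and are not affected by the start date.

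**The case against.** The strongest reply is that the sections can be read together. Safety data is wider than AEs: 8.3 includes vital signs, laboratory tests and ECGs, which Table 4 collects at Screening, and pre-dose events are still written down. On that reading, safety data start at consent, AE classification starts at first dose, and 8.2 does not contradict 8.3.6.1. Starting AE capture at first dose is also a defensible convention.

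Part of this stands. A reader might infer that the synopsis and 8.2 expressly start AE and SAE capture at consent. They do not. It is a fair reading, because 8.3 says that safety is evaluated by collecting AE information, but it is not the wording. The inconsistency does not depend on it, since 8.3.6.1 also differs from Table 4 and 8.3.6.3. A general first-dose start can be defended; having no rule for events caused by protocol procedures is harder to defend.

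A reader might also infer that pre-dose harm is never reported. The documents do not support that. Events that worsen on treatment are reported, 8.3.6.3 read alone would capture the event, and 3.5 sends information on serious or unexpected AEs to the IRB with no first-dose limit. The loss follows only if 8.3.6.1 and 8.3.6.4 prevail, and nothing in the plan says which sections do.

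Exposure is also limited: the biopsy is optional, waived after an earlier post-treatment biopsy, and restricted in minors. Nor does the platelet eligibility limit show a particular bleeding risk. It is a condition for entering the trial, not a biopsy threshold, and 9.2.4 leaves biopsies to local guidelines.

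**Conclusion.** The concern holds as an inconsistency with a specific consequence. The plan states several start points for safety capture. If 8.3.6.1 and 8.3.6.4 are followed as written, a complication of the optional pre-dose biopsy gets no AE or SAE report unless it worsens after first dose. A patient whose complication prevents dosing is the least visible, being outside the safety population as well.

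Its size can be stated only as a window of up to 30 days before dosing, in those patients who have the biopsy. A reader might want to attach a probability of at least one unreported event across the 29 planned patients. The documents give neither biopsy uptake nor a complication rate, so any such figure would come entirely from assumptions.

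The conclusion assumes that sites follow the specific AE and SAE rules over the general reporting sentence. The response-rate analysis and the two-stage design are unaffected. The point should be corrected because it concerns participant safety and reporting, but it does not threaten the efficacy inference.

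**What to change.** Reconcile the synopsis, 8.2, 8.3.6.1, 8.3.6.3, 8.3.6.4 and Table 4 to one stated start point, and adapt the scripted question in 8.3.6.1 to match.

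The simplest choice is consent for all AEs and SAEs. If the sponsor prefers first dose for AEs in general, the minimum is an explicit rule that any event related to a protocol procedure is recorded as an AE from consent, with grade and causality, and reported as an SAE if serious.

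Flag these entries as pre-treatment. The treatment-emergent definition and tables in 10.5.1 then stay as they are, and a baseline grade exists for judging worsening. List separately any such events in patients who were never dosed, since 10.1 leaves them out of the safety population.

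The cost is wording in the sections named, one CRF flag and a few more AE entries during screening. Sample size and efficacy analysis do not change.

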8.3.6.2 Clinical Laboratory Abnormalities and Other Abnormal Assessments

It is the responsibility of the Investigator to assess the clinical significance of all abnormal laboratory values. The Investigator will exercise medical judgment in deciding whether abnormal laboratory values are clinically significant and represent AEs. In some cases, significant changes within the range of normal will require similar judgment by the Investigator.

If an abnormal laboratory value or assessment is clearly related to a medically defined diagnosis or syndrome, the diagnosis or syndrome will be recorded on the AE page, not the individual laboratory values. Clinically significant abnormal laboratory values should not be listed on the AE page of the eCRF, unless clinical signs or symptoms are present.

All clinically significant abnormal laboratory results or assessments will be followed until they return to normal or become stabilized (up to 30 days after end of study drug administration).

8.3.6.3 Procedures for Assessing, Recording, and Reporting Adverse Events and Serious Adverse Events

Throughout the duration of the study, the Investigator will closely monitor each subject for evidence of drug intolerance and for the development of clinical or laboratory evidence of adverse events. All adverse events (expected or unexpected) which occur during the course of the study, whether observed by the Investigator or by the subject, and whether or not thought to be drug-related, will be reported and followed until resolution or until they become stable.

The Investigator will evaluate AEs according to the following guidelines:

- ∞ **NCI CTCAE Version 4.0.** The Investigator must assign a CTC Grade for each AE ([Appendix A](#))
- ∞ **Description of event** (if the event consists of a cluster of signs and symptoms, a diagnosis must be recorded [e.g., flu syndrome] rather than each sign and symptom)

- ∞ **Onset Date**
- ∞ **Stop Date**
- ∞ **Seriousness** (see definition of SAEs, [Section 8.3.6.1](#))

The Investigator must record whether or not the AE meets the definition of serious. If the event is serious, the Investigator must complete a Serious Adverse Event report form (see [Section 8.3.6.4](#)). CASI Pharmaceuticals or designee will monitor the completeness and accuracy of these forms.

- ∞ **Relationship to Study Medication**

The Investigator must assess the relationship between the AE and the study medication as either not related or having a possible, probable, or definite relationship to the study medication.

- ∞ **Outcome**

Outcome of AEs should be recorded based on the status of the AE at discontinuation from the study (includes 30 days post last dose) as resolved, resolved with sequelae, ongoing or death. If an AE is not resolved at the time of discontinuation, the AE should be followed until resolution (return to normal or baseline values) or until judged by the Investigator to be no longer clinically significant.

- ∞ **Action Taken** (None, AE Required Treatment, Temporarily Interrupted or Permanent Discontinuation of Study Medication)
- ∞ **Patient Status** (*i.e.*, Was patient prematurely discontinued due to AE?)

Events will be coded into one of the following causality categories as defined below:

Category	Definition
Unrelated	Clearly and incontrovertibly due only to extraneous causes, and does not meet criteria listed under possible or probable.
Unlikely	Does not follow a reasonable temporal sequence from administration. May have been produced by the subject's clinical state or by environmental factors or other therapies administered.
Possible	Follows a reasonable temporal sequence from administration, but may have been also produced by the subject's clinical state, environmental factors or other therapies administered.
Probable	Clear-cut temporal association with administration with improvement on cessation of investigational medicinal product or reduction in dose. Reappears upon rechallenge. Follows a known pattern of response to the investigational medicinal product.

Adverse events with the causality assessed as unrelated or unlikely are categorized as not related to study medication.

Adverse events with the causality assessed as possible or probable are categorized as related to study medication and are called adverse drug reactions.

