10.5.1 Adverse Events

Adverse events will be coded to system organ class and preferred term using MedDRA version 16.0 or higher. All adverse events occurring after the initiation of the study treatment (treatment emergent adverse events) will be reported, including events present at baseline that worsened during the study.

Adverse events will be summarized by treatment group to provide visual comparison among the treatment groups with respect to incidence of adverse events (the number of subjects reporting at least one episode of a specific adverse event), incidence of adverse events by severity within body system, incidence of adverse events by attribution within body system, and incidence of adverse events causing withdrawal and incidence of serious adverse events. Regarding severity and attribution summaries, the most extreme outcome (highest severity and closest to study drug related) will be used for those subjects who experience the same adverse event on more than one occasion.

Written narratives will be provided for all serious, unexpected or other significant adverse events that are judged to be of special interest because of their clinical importance.

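### Section 8.3.6.2 keeps symptom-free, clinically significant laboratory values off the AE page while 8.3.1 and 8.3.6.1 require them as AEs, so the AE tables could miss non-serious laboratory toxicity

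*Combined protocol and SAP*

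**What the plan says.** Three instructions in the combined protocol and SAP concern laboratory values that the investigator has judged clinically significant.

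- Section 8.3.1: "Clinically significant abnormal laboratory parameters occurring during the study are reported as AEs".
- Section 8.3.6.1: "Any new laboratory abnormality assessed as clinically significant by the Investigator must be recorded as an adverse event". The same section counts as AEs the "reasons for any change in medication (drug and/or dose) other than planned titration".
- Section 8.3.6.2: "Clinically significant abnormal laboratory values should not be listed on the AE page of the eCRF, unless clinical signs or symptoms are present". The sentence just before it deals with a different case: where a diagnosis or syndrome explains the value, the diagnosis goes on the AE page in place of the value.

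Downstream, Section 8.3.6.3 attaches a CTCAE grade, a causality assessment and an action taken to each AE. Section 10.5.1 tabulates AE incidence and severity, then "incidence of adverse events by attribution within body system, and incidence of adverse events causing withdrawal", and covers treatment-emergent events "including events present at baseline that worsened during the study". Section 10.5.2 separately summarises laboratory results with descriptive statistics and shifts from baseline.

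**The concern.** One of the secondary objectives (Section 5.2) defines the safety of ENMD-2076 through how often AEs occur and how severe they are. That result is only as complete as the AE page. If one site enters a symptom-free abnormality because 8.3.1 and 8.3.6.1 tell it to, and another leaves it off because 8.3.6.2 tells it to, the two contribute differently to the same table and the pooled incidence depends on which sentence each site read.

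The matter is relevant to this drug. Section 4.3.1 names elevated liver function tests, hyponatremia and neutropenia among earlier serious events, and decreased platelets among other Phase 2 events. All four are found by laboratory tests and can occur without symptoms, although the section does not say whether the earlier cases did.

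**Working it through.** The point rests on a comparison of text; the plan states no figure to reproduce. Take a laboratory value already judged clinically significant and apply each rule.

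| Situation | 8.3.1 | 8.3.6.1 | 8.3.6.2 |
|---|---|---|---|
| Signs or symptoms present | AE | AE if new | May be listed |
| Explained by a diagnosis | AE | Record the diagnosis if available | Record the diagnosis |
| No symptoms, no linked diagnosis | AE | AE if new | Not listed |

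The first two rows can be reconciled. In the third, a site cannot obey all three sections.

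1. **Does the diagnosis sentence resolve it?** No. It stands apart from the disputed sentence, whose only exception is symptoms. It also leaves open whether an isolated low neutrophil count or low sodium is a diagnosis (neutropenia, hyponatremia) or merely a value.
2. **Does investigator judgment resolve it?** No. Section 8.3.6.2 leaves to judgment whether a value is significant and represents an AE, but 8.3.6.1 removes the choice once a new value has been judged significant.
3. **A concrete case.** A symptom-free, drug-related Grade 3 laboratory toxicity calls for a dose hold and then a reduction under Section 7.4. As the reason for an unplanned dose change it is an AE under 8.3.6.1, yet 8.3.6.2 keeps it off the AE page.
4. **What is lost if 8.3.6.2 is followed.** The event is absent from the incidence, severity and attribution tables in 10.5.1. The value itself survives in 10.5.2, but that section specifies neither attribution nor action taken.
5. **What is not lost.**
   - Serious events go through their own form and portal (Sections 8.3.6.3 and 8.3.6.4); the disputed sentence restricts only the AE page.
   - The reason for discontinuation is documented under Section 6.3.3.
   - Clinically significant results are followed until normal or stable, up to 30 days after study drug ends (Section 8.3.6.2).
   - The action-taken options after none are "AE Required Treatment, Temporarily Interrupted or Permanent Discontinuation of Study Medication". There is no dose-reduction option, so a reduction would not be captured in that field even if the AE were entered.

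**Size.** The change in a term's incidence is (patients omitted)/(patients in the safety population). With all 29 planned patients dosed, one omitted patient is 1/29 = 3.4 percentage points. The documents give no rate of symptom-free events. Purely as an assumed range, 3 patients would be 3/29 = 10.3 points and 5 would be 5/29 = 17.2 points. These figures show sensitivity and do not estimate the undercount.

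**The case against.** The strongest reply is that the practical effect is likely to be small. Two of the three provisions require recording, and 8.3.6.1 says must where 8.3.6.2 says should not. Section 8.3.6.1 asks for diagnoses where available, and Section 4.3.1 already names neutropenia and hyponatremia as events, so many sites would naturally enter them. Section 10.7 promises that CRF completion will be explained to investigators and that monitors will check completeness and consistency.

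Much of this stands. It rules out saying that laboratory toxicity *will* be undercounted: an omission needs a site to follow 8.3.6.2, and a difference between sites needs them to choose differently. It does not remove the contradiction. The CRF instructions are not in the documents, and a monitor checking consistency has two opposing rules to check against.

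A reader might also infer that such events vanish from every safety output, serious events and withdrawals included. The documents do not support that, given the separate routes listed above. Nor is the phrase in 8.3.6.3 about monitoring "for the development of clinical or laboratory evidence of adverse events" a further contradiction, since laboratory evidence can support a diagnosis.

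**Conclusion.** The contradiction is real, is in the current text, and should be corrected. Its consequence is conditional: where a site follows 8.3.6.2, symptom-free, clinically significant laboratory toxicity with no linked diagnosis could be missing from the AE incidence, severity and attribution tables, mainly for non-serious events. The direction is clear, because that site would record fewer laboratory AEs than one following 8.3.1 and 8.3.6.1. The total cannot be estimated; 3.4 points per omitted patient assumes 29 treated patients. Confidence is high for the conflict of wording and lower for how sites would act on it. The overall response rate and its decision rule are unaffected.

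Two further inferences should be resisted. Counting the laboratory-defined terms in Section 4.3.1 says nothing about how many patients would be omitted. And the mention there of acute asymptomatic pancreatitis does not make a pancreatic enzyme test part of this point: the section gives neither count nor causality, and what to monitor is a separate question from how findings are recorded.

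**What to change.** Replace the disputed sentence in 8.3.6.2 with:

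> Any laboratory abnormality that is new or has worsened from baseline and is judged clinically significant by the Investigator is recorded as an AE, with or without symptoms; where a diagnosis or syndrome explains it, the diagnosis is recorded.

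The reference to worsening is needed because Section 6.3.1 admits patients with AST and ALT up to 5 times the upper limit of normal and 10.5.1 counts baseline events that worsen. Add that a value leading to a hold, reduction or discontinuation under Section 7.4 is clinically significant, and put the same rule in the CRF completion instructions.

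For patients already entered, list laboratory values of Grade 3 or higher and laboratory-driven dose changes that have no AE record, and query the sites.

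The cost is a minor amendment, some site queries, and more laboratory AE entries, which 8.3.1 and 8.3.6.1 already largely require. No visit or blood draw is added. No dosing rule changes, because Section 7.4 acts on the toxicity and its grade and not on whether the event is on the AE page.
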